Cabergoline for Lactation Inhibition After Second-Trimester Abortion or Loss (LISTA)

Study Protocol and Statistical Analysis Plan

NCT04701333

January 13, 2021

Cabergoline for Lactation Inhibition after Second-Trimester Abortion or Loss

Telephone: Email:

1. Brief Summary

Breast pain following second-trimester abortion is common. (Hagey 2020, Andersen 1990) Breast engorgement and milk leakage following second-trimester perinatal loss and abortion can cause both physical pain and emotional distress. (Seresheti 2016) Dopamine agonists have previously been shown to be effective in lactation inhibition for third-trimester fetal/neonatal loss or contraindications to breastfeeding. (Tulloch 2019) In a head-tohead trial, cabergoline was more effective with a better safety profile than bromocriptine and has thus emerged as preferred treatment for term lactation inhibition internationally. (Harris 2020, Giorda 1991, European 1991) Despite the frequency of breast symptoms after second-trimester abortions, there are no current guidelines for this population.

We will conduct a double-blinded, placebo-controlled, superiority trial of those undergoing abortion or intrauterine fetal demise between 18 and 28-weeks gestation at Stanford Health Care. Participants will be randomized to either cabergoline 1mg or placebo the day of procedure. Participants will complete a survey to assess symptoms, using the validated Bristol Breast Symptoms Inventory, and side-effects at baseline and Day 2, 3, 4, 7, and 14 after the procedure. (Bristol 1966) Our primary outcome is breast symptoms on Day 4. Secondary outcomes include satisfaction, acceptability, and side-effects. We hypothesize that cabergoline is superior to placebo for preventing breast engorgement after second-trimester abortion or loss. We estimate that 32 subjects in each group are required to show a 30% decrease in those reporting breast symptoms compared to the control group, with a power of 0.8 and an alpha of 0.05. We plan to recruit 100 subjects, anticipating 30% missing data and loss to follow up. Electronic, online surveys regarding breast symptoms and side-effects will be sent via text message. (Friedlander, 2020) A sub-study of 10 participants will return for serum prolactin levels on Days 2, 4, 7, 14.

This study has the potential to improve overall patient experience by validating the routine use of cabergoline for lactation inhibition after second-trimester abortion or loss.

2. Background

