The safety of bromocriptine for lactation inhibition was called into question in 1984, when the US Food & Drug Administration (FDA) called attention to reports of postpartum hypertension, seizures, and strokes associated with the use of bromocriptine. (Rayburn 1996). While no studies found an increased incidence of these events compared to placebo or anticipated postpartum incidence, the FDA ultimately asked the manufacturer in 1990 to voluntarily stop selling bromocriptine as a lactation suppressant.

In addition to the existing data showing safety of cabergoline, there is theoretic biologic plausibility as to why cabergoline is better tolerated than bromocriptine. Cabergoline has a greater affinity for D2 receptors, longer plasma half-life, and flat plasma drug concentration resulting in a shorter required duration of therapy compared to bromocriptine. (Rains 1995) Notably, in Canada, the UK, and France, cabergoline has an approved indication for the prevention of physiologic postpartum lactation.

3. Research Questions

We are aiming to answer whether cabergoline is superior to placebo at preventing breast symptoms after secondtrimester abortion or loss. The goal is to improve patient experience and establish a standard of care for lactation inhibition after second-trimester abortion or loss.

Our primary outcome is breast symptoms on Day 4 post-abortion/ post fetal expulsion. Secondary outcomes include initiation of milk secretion, satisfaction, acceptability, and side-effects.

We will test the following hypotheses:

1. A smaller proportion of those receiving cabergoline will report breast symptoms on Day 4 compared to placebo.

2. Prolactin levels will be significantly lower on Day 4 in those receiving cabergoline compared to placebo.

3. The proportion of participants ever reporting secretion of milk within 14 days post-procedure will be lower in those receiving cabergoline compared to placebo.

4. Participants receiving cabergoline will be more satisfied with their post-procedure breast symptoms compared to those receiving placebo.

5. Side-effects will occur in less than 10% of patient and not differ between those receiving cabergoline compared to placebo.

4. Methods

4A. Research Design and General Methodological Approach

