Those in the serum sub-study will have a prolactin level drawn at the time of intravenous (IV) insertion. Rhogam will be provided if indicated.

Within 4 hours of fetal expulsion and prior to discharge, the study coordinator will distribute the study drug or placebo as randomized on Day #0. All participants will receive standard information on support bras, analgesics, and cold compacts.

Days # 2-14 - Follow-up

Electronic, online surveys regarding breast symptoms using the Bristol Breast Inventory, 7 point Likert Scale to assess bother of symptoms, current bleeding profile (Janssen 1995) and side-effects will be collected on Days 2, 3, 4, 7, 14. Additionally, participants will be asked on Day 14 to rate overall acceptability of the protocol, likelihood to recommend to a friend, and willingness to pay. Surveys will be sent via text message over RedCap at 08:00. (Friedlander 2020) A phone call will be made to participants between 17:00-20:00 if the survey is not completed that day. Day 14 survey will include measures of willingness to pay and overall satisfaction.

A substudy of 10 patients enrolled at Stanford (5 cabergoline, 5 placebo) will return to Stanford laboratories for repeat serum prolactin levels on Day 2, 4, 7, 14.

An electronic gift card will be sent to the participant after 14 days. Participants will receive **\$** per survey completed with a **\$** bonus for completing all five surveys on-time for a maximum of **\$** for full participation. Those participating in the serum prolactin sub-study will receive **\$** per phlebotomy session with a bonus **\$** for completing all lab draws on the appropriate day for a maximum of **\$** for full participation. With consent, the gift card will be distributed by e-mail or mobile phone number via Amazon. For patients who prefer a physical gift card, it will be mailed to their reported address. Participants will have the opportunity to forego gift certificate and donate funds to a reproductive health organization.

4B. Criteria for selection of subjects

Inclusion:

Pregnant people, ages 18 years or older

Intrauterine pregnancy between 18/0-28/0 weeks of gestation age (by ultrasound dating performed prior to or same day of enrollment visit)

Consented for an induced, elective abortion or undergoing induction for demise

English or Spanish speaking

Able to consent for a research study, literate in English or Spanish

Willing to comply with study procedures and follow-up

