Stanford University has a license for the RedCap data management system. (Harris 2009) REDCap is a web-based application that is secure, reliable, and HIPAA-compliant for storing research study data. REDCap is designed with built-in features to address confidentiality and compliance requirements. Electronic, online surveys will be sent via text message over RedCap on Days 2, 3, 4, 7, 14. Data associated with patient health identifiers (PHI), including the signed informed consent, will be collected electronically. REDCap allows for easy data download into SAS or other statistical software programs. No data will be collected on paper forms. SAS OnDemand will be used for data analysis. Data will be analyzed with parametric or non-parametric statistical tests, as appropriate. Stratified analysis and logistic regression will be performed to assess demographic characteristics as predictors of breast symptoms and associate distress.

A Data and Safety Monitoring Committee (DSMC) will be used given that the use of cabergoline for lactation inhibition is a new and unfamiliar intervention and limited data exists for this use. A DSMC will be formed to monitor the progress of the study and review any of the following events under the Data and Safety Monitoring Plan: (i) Adverse events and/or serious adverse events will be recorded in our data collection tool, REDCap (ii) The research coordinator will be responsible for directly monitoring the data and compliance with the protocol. All events will be immediately reported to the principal investigator/sponsor. The sponsor will be responsible for reporting any adverse or serious adverse events to the DSMC members and IRB (iii) Serious adverse events and unanticipated problems will be reported immediately to the monitoring committee and any events of stroke, hospitalization for hypertensive emergency, hospitalization for psychiatric condition will lead to immediate termination of the study (iv) Side-effects that are common according to the FDA package insert including nausea/vomiting, headache, dizziness, orthostatic hypotension, constipation, abdominal pain, fatigue will be reported to the IRB by the principal investigator. All adverse events will be summarized with special attention to events that may be related to the study drug.

5. Study Population

Number of Subjects and Statistical Power

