Incidence of symptomatic breast engorgement after second-trimester abortion has been reported to occur between 50-91% of individuals (Hagey 2020, Anderson 1990). In prior studies of term lactation inhibition using

cabergoline 1 mg, complete absence of lactation was noted in 78-100% of study subjects (European 1991, Mellis 1998, Giorda 1991, Caballero 1991). We estimate that 41 subjects in each group are required to show a 30% decrease in those reporting breast symptoms compared to the control group, with a power of 0.8 and an alpha of 0.025 (planned interim analysis). We plan to recruit 100 subjects, anticipating 10% missing data and loss to follow up.

Based on the prior RCT comparing bromocriptine to placebo after second-trimester abortion, the mean serum prolactin level in the placebo group was $44\pm8 \mu g/L$ on Day 4 and $12.2\pm2 \mu g/L$ in the bromocriptine group (Andersen 1990). The upper-limit of normal for a non-lactating female-assigned at birth is 23 $\mu g/L$. We will need 8 patients to have a 90% chance of detecting, at the 5% significance level, a decrease in serum prolactin from 44 in the control group to 23 in the experimental cabergoline group. We will recruit 10 subjects, anticipating 20% loss to follow up and missing data.

Locations

Patients will be recruited at Stanford Gynecology Clinic in Palo Alto, CA. Stanford University is a large tertiary care center with patients referred from the seven Perinatal Diagnostic Centers (PDCs) across Northern California with fetal anomalies as well as local practices and Planned Parenthood Mar Monte California. Medicaid covers abortion care through 23/6 weeks. In 2019, we performed 72 abortions between 18/0 and 23/6 weeks gestation at Stanford University and the Lucille Packard Childrens Hospital admitted an average of 1 patient each month for medical abortion or fetal demise between 18-28 weeks gestation.

6. Timeline

With an anticipated 66% enrollment, we anticipate enrollment to take 19 months.

| Year 1 | Sept-20 | Oct-20 | Nov-20 | Dec-20 | Jan-21 | Feb-21 | Mar-21 | April-21 | May-21 | June-21 | |
|---------------------|---------|--------|---------|--------|--------|--------|--------|----------|--------|----------|--------|
| Consent development | х | Х | | | | | | | | | |
| Survey development | Х | Х | | | | | | | | | |
| IRB review | | Х | х | х | | | | | | | |
| Recruitment | | | | | Х | Х | х | Х | Х | Х | |
| Data collection | | | | | х | х | х | х | х | х | |

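### No analysis method is stated for missing Day 4 answers, and the Bristol answers from baseline and Days 2, 3 and 7 have no role in the primary test; the cost is small near 10% missing and noticeable near 30%

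*Combined protocol and SAP*

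**What the plan says.** The primary hypothesis in section 3 is a single-day comparison of proportions: "A smaller proportion of those receiving cabergoline will report breast symptoms on Day 4 compared to placebo".

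Missing data are expected, but two figures are given:
- Section 5: "We estimate that 41 subjects in each group are required to show a 30% decrease in those reporting breast symptoms", at alpha 0.025 and power 0.8, followed by "We plan to recruit 100 subjects, anticipating 10% missing data and loss to follow up".
- Brief Summary: "We estimate that 32 subjects in each group are required to show a 30% decrease", at alpha 0.05 and power 0.8, followed by "We plan to recruit 100 subjects, anticipating 30% missing data and loss to follow up".

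On analysis, section 4F says "Data will be analyzed with parametric or non-parametric statistical tests, as appropriate" and adds a logistic regression on demographic predictors. It gives no primary model, analysis set, missing-data method or sensitivity analysis.

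On data collection, section 4A takes a baseline Bristol questionnaire on Day 0 and then "Electronic, online surveys regarding breast symptoms using the Bristol Breast Inventory" on Days 2, 3, 4, 7 and 14. It also provides an evening phone call when that day's survey has not been completed, payment for each survey and a bonus for completing all five on time.

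**The concern.** A two-group test of one day's answers, with no rule for absent ones, drops whoever did not answer on Day 4. That is unbiased for the risk difference only if, within each arm, answering on Day 4 is unrelated to having symptoms. If symptomatic participants answer less (or more) often, both arms' rates shift, and the shifts need not cancel when the true rates differ.

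Someone who misses only Day 4 may have answered Day 3 or Day 7, and those answers are informative about Day 4. Nothing in the plan uses them. The accuracy of the primary estimate and some power are at stake. So is the freedom to choose a missing-data method after the data have been seen.

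**Working it through.** **Step 1. The plan's own sample size.** The control rate, the sidedness and whether the 30% decrease is absolute or relative are not stated. Assume a 30-point absolute decrease and 1:1 allocation, with

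n per group = [z_α √(2p̄(1−p̄)) + z_β √(p₁(1−p₁) + p₂(1−p₂))]² / (p₁−p₂)².

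For 88% v 58% at two-sided 0.025: p̄ = 0.73, so [2.241 × √0.3942 + 0.842 × √0.3492]² / 0.09 = 40.3, giving 41. One-sided 0.025 with 75% v 45% also gives 41. For the Brief Summary, 90% v 60% at two-sided 0.05 gives 32. Both stated figures can be reproduced.

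**Step 2. Does recruiting 100 cover the stated losses?**
- Section 5: 2 × 41 = 82; 82/0.90 = 91.1, so 92.
- Brief Summary: 2 × 32 = 64; 64/0.70 = 91.4, so 92.
- Mixed pairing, which the documents never make: 82/0.70 = 117.1, so 118.

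Each section's own pairing fits within 100. With 10% missing (45 per arm), power is 0.84 to 0.87 under the inputs that reproduce or nearly reproduce 41. With 30% missing (35 per arm) it is 0.83 to 0.84 at alpha 0.05, but 0.73 to 0.76 at alpha 0.025.

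**Step 3. Bias of a responder-only test when non-response depends on Day 3.** Assumptions, none of them in the documents: a latent Day 3–Day 4 correlation of 0.84, equal symptom rates on the two days, and Day 4 non-response of 15% without Day 3 symptoms and 40% with them. Let p₁₁ be the probability of symptoms on both days. Among responders,

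rate = [0.60 p₁₁ + 0.85 (p − p₁₁)] / [1 − 0.40p − 0.15(1−p)].

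- 90% v 60%: p₁₁ = 0.861 and 0.512. Placebo: (0.516 + 0.033)/0.625 = 0.880. Cabergoline: (0.307 + 0.075)/0.700 = 0.546. The difference is 0.334 against a true 0.30. Missing: 37.5% and 30%, mean 34%.
- 50% v 20%: p₁₁ = 0.409 and 0.137. Placebo: 0.445. Cabergoline: 0.170. The difference is about 0.276. Missing: 27.5% and 20%, mean 24%.

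Scaling both non-response rates down to 10% missing overall gives 0.308 (90 v 60), 0.304 (75 v 45) and 0.292 (50 v 20), so the bias is at most 0.008.

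**Step 4. What the other days recover.** Simulation with 100 participants, two-sided 0.025 and 2,500 trials per scenario; 96% of Day 4 non-responders had answered Day 3 or Day 7.

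| Scenario | Responders only | Imputed from arm and Days 2, 3, 7 |
|---|---|---|
| 90 v 60, Step 3 mechanism: difference | 0.333 | 0.298 |
| 90 v 60, Step 3 mechanism: power | 85% (raised by the bias) | 83% |
| 50 v 20, Step 3 mechanism: difference | 0.277 | 0.296 |
| 50 v 20, Step 3 mechanism: power | 69% | 76% |

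With random missingness of 10 to 20%, the standard error falls by 1 to 4% and power rises by about 1 to 3 points (for example 72.1% to 74.7% at 75 v 45).

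A second simulation (75 v 45, one-sided 0.025, latent correlation 0.6 to 0.8, 30% missing) gave about 0.74 to 0.77 for responders only. Imputation gave 0.80 to 0.82 when the other days were available, and only 0.72 to 0.77 when non-responders had missed every day. With no treatment effect, rejection rates were 0.031 to 0.034 with imputation and 0.025 to 0.030 without. A small part of the gain may therefore come from a slightly liberal test.

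**Step 5. Non-response that depends on the unseen Day 4 answer.** Suppose symptomatic participants are twice (or half) as likely not to answer, equally in both arms. At 30% missing, 90 v 60 then gives 0.334 (0.243); at 10% it gives 0.309 (0.286). With no treatment effect this mechanism gives zero bias. If the ratio is 2 in one arm and one half in the other, the bias with no effect (60% in both arms) is about ±0.035 at 10% missing and ±0.15 at 30%.

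**The case against.** Four stronger readings are tempting, and the documents support none of them.

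- A reader might infer that the plan loses its stated power. Step 2 shows that 100 covers each section's own pairing. A shortfall appears if 30% missing is joined to alpha 0.025, or if a mid-range control rate is combined with a two-sided 0.025 test. At 45 per arm the latter gives 75.7% at 75 v 45 and 78.3% at 50 v 20. The plan states neither combination.
- A reader might infer that extra enrolment is the only measure against missing data. Section 4A also has the same-day call and the payments, which may keep non-response low.
- A reader might infer that the plan commits to a responder-only test. Section 4F is silent. Dropping non-responders is the default of the tests it names, not a stated choice.
- A reader might treat 10 to 30% as a planned range. It is two conflicting statements.

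It is also fair to say that the bias in Step 3 needs 24 to 34% missing, well above section 5's 10%. That simulation also favours its remedy, because non-response is driven by a variable in the imputation model and almost everyone has an adjacent answer. People lost to follow-up have few such answers, and there the gain nearly vanishes. A treatment effect alone does not make non-response depend on symptoms.

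These points limit the size of the problem. They do not supply the missing method, and they do not explain why answers already collected should be left out.

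**Conclusion.** The point holds as a modest, inexpensive improvement to the analysis plan. No method for missing Day 4 answers is specified, and the adjacent Bristol answers are unused in the primary comparison.

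If section 5's 10% is realised, little is lost. If missingness is nearer the Brief Summary's 30% and follows Day 3 symptoms, a responder-only estimate overstates a 0.30 difference by about 0.03 at a high control rate and understates it by about 0.02 at a low one. In the low-rate case about 7 power points are also lost (69% v 76%).

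These sizes depend on the assumed control rates, correlation, non-response rates and availability of adjacent answers. Imputation from other days corrects the part of non-response that observed answers explain. It cannot be relied on for dependence on unseen Day 4 symptoms, which needs its own sensitivity analysis.

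**What to change.** 1. Reconcile the missing-data fraction, sample size and alpha between the Brief Summary and section 5.
2. State in section 4F that the primary estimand is the Day 4 risk difference in all randomised participants.
3. Estimate it by multiple imputation of missing Day 4 status from arm, baseline Bristol score and the Day 2, 3 and 7 responses, or by an equivalent arm-by-day repeated-measures logistic model with the Day 4 contrast as the test. Check the type I error of the chosen method at the planned size before fixing it.
4. Report the complete-case comparison, and a sensitivity analysis that lets non-response depend on the unseen Day 4 answer, including by different amounts in the two arms.

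The cost is about a paragraph of plan and a little programming, with no new data. The downside is reliance on data being missing at random given the other days. Little is recovered for participants who miss every survey.

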There is both biologic plausibility and existing evidence that a dopamine agonist can antagonize prolactin release which then leads to cessation of lactogenesis.

Early research showed bromocriptine 2.5mg twice daily for two weeks after second-trimester abortion caused a significant reduction in breast tenderness, milk secretion, and serum prolactin levels on day 4 compared to placebo. (Andersen 1990) Prolactin levels were suppressed more effectively with bromocriptine with 89% achieving serum prolactin levels less than 23 micrograms/L on day 4 as compared to only 28% with placebo.

Bromocriptine (0.25mg twice daily for 14 days) was then compared to cabergoline (1mg once, day of procedure) in a large, multi-center randomized control trial after term delivery. (European 1991) On postpartum day 3, a complete absence of breast symptoms was reported in 90.4% of individuals in the cabergoline group and 83.8% in the bromocriptine group. Cabergoline continued to be superior for the entire observation period of 21 days where an absence of symptoms was significantly better with cabergoline (74%) than with bromocriptine (51%). In a substudy where serum prolactin levels were measured up to 21 days after delivery, the initial drop in mean prolactin levels was more dramatic from delivery to day 2 for cabergoline (131.3 μ g/L to 26.3 μ g/L) compared to bromocriptine (129.9 μ g/L to 45.5 μ g/L). Bromocriptine also showed a considerable prolactin rebound after day 15 which was not observed in the cabergoline group.

In a dose-finding study comparing a single dose of cabergoline 1mg, 0.75mg, 0.5mg or placebo after term delivery resulted in complete absence of breast symptoms in 90%, 70%, 45%, 20%, respectively of participants up to day 14 postpartum. (Caballero 1991) Similarly, a dose-finding study of a single dose of cabergoline 0.8mg, 0.6mg, 0.4mg or placebo after term delivery reported no milk secretion in 100%, 100%, 50%, 12.5%, respectively (Mellis 1998). Prolactin levels dropped significantly for the three experimental doses compared to the placebo group on days 1-3 postpartum.

2G. Current uses of cabergoline for lactation inhibition

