Access to smart phone throughout study

Exclusion:

Prior mastectomy (breast reduction or chest masculinization surgery acceptable)

Currently breastfeeding

Currently receiving dopamine agonist therapy for other indication (prolactinoma, Cushings syndrome, acromegaly, restless leg syndrome)

Contraindication to cabergoline (as per package insert)

- Uncontrolled hypertension defined as baseline BP > 150/100, or chronic hypertension requiring more than one baseline medication, or pregnancy-induced hypertension spectrum disorders (gestational hypertension, preeclamspia, eclampsia)
- History of cardiac valvular disorders or valvular repair
- History of pulmonary, pericardial, or retroperitoneal fibrotic disorders

• Current use of D2 antagonists (phenothiazines, butyrophenones, thioxanthenes, or metoclopramide)

4C. Subject Recruitment and Allocation

Subjects will be recruited from Stanford Gynecology Clinic on the day of their Family Planning consultation, after consent for but prior to abortion or the Lucille Packard Childrens Hospital Labor & Delivery after diagnosis of intrauterine fetal demise. Only patients in the appropriate gestational ages will be approached. Potential participants will be screened for the study and if eligible and willing to participate in the project, they will be consented for the study.

4D. Description of Drugs and Devices

Cabergoline is a long-acting dopamine receptor agonist with a high affinity for D2 receptors. It is FDA approved for the treatment of hyperprolactinemic disorders, either idiopathic or due to pituitary adenomas (FDA package insert). We will be using cabergoline off-label.

4E. Laboratory and Other Investigations

A substudy of 10 participants (5 cabergoline, 5 placebo) will return to Stanford laboratories for repeat serum prolactin levels on Day 2, 4, 7, 14. The Stanford laboratory runs serum prolactin on a electrochemiluminescence immunoassay with a working range of was $0.5-150 \mu g/L$ and interassay coefficient of variation is 4.68%. The reference range in this lab for non-pregnant, non-lactating female-assigned at birth is $4.8-23.3 \mu g/L$.

4F. Data Management & Analysis

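### Day 4 prolactin figures in Sections 2F and 5 cannot both hold if ± is an SD, so the sub-study's claim of 90% power with 8 patients is unsupported until they are reconciled

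*Combined protocol and SAP*

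**What the plan says.** Section 3 lists as hypothesis 2: "Prolactin levels will be significantly lower on Day 4 in those receiving cabergoline compared to placebo".

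Section 5 (Number of Subjects and Statistical Power) sizes the comparison. From an earlier bromocriptine trial it takes Day 4 values of 44±8 µg/L under placebo and 12.2±2 under bromocriptine. It then states: "We will need 8 patients to have a 90% chance of detecting, at the 5% significance level, a decrease in serum prolactin from 44". The cabergoline value to be detected is 23, which Section 5 gives as the top of the normal range. On recruitment it says: "We will recruit 10 subjects, anticipating 20% loss to follow up and missing data". Section 4E gives the split: "A substudy of 10 participants (5 cabergoline, 5 placebo) will return to Stanford laboratories for repeat serum prolactin levels".

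Section 2F describes the same bromocriptine trial on the same day, "with 89% achieving serum prolactin levels less than 23 micrograms/L on day 4 as compared to only 28% with placebo".

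The protocol never says whether ± is a standard deviation or a standard error, whether the test is one- or two-sided, or how large the groups in the cited trial were.

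**The concern.** Sections 2F and 5 describe one set of Day 4 measurements in two ways: by mean and spread, and by the share below 23. The two descriptions imply very different spreads. A placebo group with mean 44 and SD 8 has its threshold 2.6 SDs below the mean, yet more than a quarter of that group is said to lie below it.

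The sample size depends on that spread. If it is understated, hypothesis 2 is presented as a test with 90% power when the real figure may be far lower. A non-significant Day 4 result from 8 to 10 patients could then be read as evidence against a 44-to-23 difference.

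**Working it through.** **Inputs.** Section 5: means 44 and 12.2, ± values 8 and 2, target 23 (difference 21), 90% power, 5% level, 8 evaluable, 10 recruited. Section 4E: equal allocation. Section 2F: 28% (placebo) and 89% (bromocriptine) below 23.

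**1. Reproducing the plan's figure with SD = 8.** n per arm = 2·SD²·(1.960 + 1.282)²/21² = 3.05, rounded up to 4, so 8 in total; 8/(1 − 0.20) = 10. Both stated numbers are recovered. Power at 4 per arm is 96% by the normal approximation. By t-test it is 86.9% two-sided and 94.6% one-sided.

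**2. Are the two passages compatible?** For any distribution with mean μ and SD σ, the share lying at least d away on one side is at most σ²/(σ² + d²) (one-sided Chebyshev, or Cantelli, bound). This also holds for an observed sample; an n − 1 divisor in the SD only tightens it.

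- Placebo, d = 44 − 23 = 21: 64/(64 + 441) = 12.7% at most below 23. Stated: 28%.
- Bromocriptine, d = 23 − 12.2 = 10.8: 4/(4 + 116.64) = 3.3% at most at or above 23. Implied: 100 − 89 = 11%.

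Rounding does not explain the gap. With mean 43.5 and SD 8.49 the placebo limit is 14.6%; with mean 12.25 and SD 2.49 the bromocriptine limit is 5.1%.

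**3. Spread needed to fit the percentages.** The smallest possible SD is d·√(p/(1 − p)).

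- Placebo: 21·√(0.28/0.72) = 13.1. Normal shape: 21/0.583 = 36.0. Lognormal: about 34.8.
- Bromocriptine: 10.8·√(0.11/0.89) = 3.8. Normal shape: 10.8/1.227 = 8.8. Lognormal: about 10.4.

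**4. Spread that 90% power allows.** By t-test at 4 per arm, the common SD must be at most 7.6 (two-sided) or 8.9 (one-sided). A placebo SD of 13.1 with no spread at all under cabergoline has root mean square 13.1/√2 = 9.26, above both limits.

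**5. Power for 44 versus 23.** The documents give no spread for cabergoline, so bromocriptine's is borrowed: as an SD in the two-point and normal rows, and as a log-scale SD in the lognormal row.

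| Assumption | 4 per arm, two-/one-sided | 5 per arm, two-/one-sided |
|---|---|---|
| SD 8 in both arms | 87% / 95% | 95% / 98% |
| Percentages right, minimum SDs 13.1 and 3.8 (two-point distributions, exact enumeration) | 66% / 69% | 73% / 84% |
| Percentages right, normal, SDs 36.0 and 8.8 (root mean square 26.2) | 16% / 26% | 20% / 31% |
| Same, simulated with unequal SDs | 20% / 29% | 23% / 34% |
| Percentages right, lognormal (log SDs 0.70 and 0.74), test on log scale | 20% / 32% | 26% / 39% |

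On the raw scale the lognormal case has lower two-sided power, about 14.5% and 19%. If the placebo SD of 36.0 applied to both arms, two-sided t-test power would be about 11% and 13%. The rows based on the percentages are illustrations, not bounds.

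**The case against.** The strongest reply accepts the incompatibility and disputes its size and weight.

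- **The low power figures come from chosen shapes.** This stands. Section 2F does not by itself imply 20% power, and the normal model with SD 36 would put 11% of prolactin values below zero. Across the cases above the range runs from 11% to 84%. The favourable end needs two-point distributions, which the documents give no reason to expect, and even there 90% is not reached.
- **The standard-error explanation is only suggestive.** Under a normal shape the implied SDs are 36.0/8 = 4.5 and 8.8/2 = 4.4 times the ± values, a similar ratio in both arms. Under a lognormal shape the ratios are 34.78/8 = 4.35 and 10.43/2 = 5.21, which agree less well. A standard error fits but is not shown.
- **The percentages may come from other patients.** This is possible. Section 2B says the cited trial also had a no-treatment arm and reports symptoms for the placebo and no-treatment groups together. Section 2F, however, attributes the 28% to placebo alone.
- **The target of 23 is conservative.** If cabergoline matched bromocriptine's 12.2 (difference 31.8), power under root-mean-square SD 26.2 would be 30% (39%) two-sided and 45% (54%) one-sided for 4 (5) per arm. That is better, still far below 90%, and not the comparison Section 5 states.
- **The practical weight is small.** Agreed: prolactin is not among the secondary outcomes listed in Section 3, and nothing in the plan says a null result would be judged against 90% power. Section 5 nonetheless attaches that figure to a stated hypothesis.

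**Conclusion.** The concern holds: the power statement is wrong as written, and the matter is minor. The contradiction needs no distributional model. It rests on two assumptions: that ± is an SD, the reading that reproduces 8 patients, and that both sections describe the same patients on Day 4, as the shared citation, day and threshold indicate.

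No reading leaves the claim as it stands:

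- **± is an SD:** Section 2F's percentages are misquoted or come from other patients. The t-test power at 4 per arm then falls just short of 90% two-sided and exceeds it one-sided, and the plan does not say which applies.
- **± is a standard error:** the two sections can agree, but 8 is then the wrong input.
- **The percentages are right for these patients:** 90% is not reached in any case examined.

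Confidence is high in the inconsistency and low in any particular replacement power figure. Only the prolactin sub-study is affected.

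**What to change.** Check in the cited trial report (a) whether ± is an SD or a standard error, and the group sizes; and (b) whether 28% and 89% below 23 are quoted correctly and refer to the same patients as the means. Correct Section 2F or Section 5 accordingly and label the ±.

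Then replace the 90% statement with the power at 8 to 10 patients, using the verified SD and a stated sidedness. Keep 10 participants, and state that the Day 4 difference will be reported with a 95% confidence interval, so that a non-significant result is not read as a well-powered negative.

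The cost is one look at the source and a few sentences in Sections 2F and 5. Sample size, blood draws and conduct do not change, though the stated power may become less favourable.
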